
Section 9.8 Interim Analyses
	
<del>There are no planned interim efficacy analyses.</del>
	
An interim analysis will be conducted at Week 52 in which all efficacy and safety endpoints will be assessed as described above. A clinical study report will be generated based on these data to support submission of 1-year data.
	
Clarified plan to conduct two analyses (one with data through 52 weeks of treatment and one with data through 104 weeks of treatment) and develop a separate clinical study report for each analysis.

Section 10.1.6 Electronic Case Report Forms
	
For each patient enrolled, an eCRF must be completed as specified in the <del>Study Reference Manual</del>.
	
For each patient enrolled, an eCRF must be completed as specified in the Investigator Site File.
	
Updated referenced document.

Section 10.2.3 Study Report
	
A clinical study report will be prepared and provided to the regulatory authority(ies).
	
A clinical study report will be prepared and provided to the regulatory authority(ies) at Week 52 and a second clinical study report will be prepared at the end of the study (Week 104).
	
Clarified plan to conduct two analyses (one with data through 52 weeks of treatment and one with data through 104 weeks of treatment) and develop a separate clinical study report for each analysis.

## LIST OF ABBREVIATIONS

---

Term	Explanation
ALT	alanine aminotransferase
AST	aspartate aminotransferase
BP	blood pressure
CBC	complete blood count
CFR	Code of Federal Regulations
CI	confidence interval
COVID-19	novel coronavirus 2019
CTCAE	Common Terminology Criteria for Adverse Events
DHEA	dehydroepiandrosterone
DTP	direct-to-patient
DXA	dual-energy x-ray absorptiometry
ECG	electrocardiogram
eCRF	electronic Case Report Form
eDiary	electronic diary
EHP	Endometriosis Health Profile
EQ-5D-5L	European Quality of Life Five-Dimension Five-Level Scale
EU	European Union
FDA	(United States) Food and Drug Administration
GCP	Good Clinical Practice
GnRH	gonadotropin-releasing hormone
HR	heart rate
ICH	International Council on Harmonisation
ID	identification
IEC	Independent Ethics Committee
INR	international normalized ratio
IRB	Institutional Review Board
IVRS	interactive voice response system
IWRS	interactive web response system
MedDRA	Medical Dictionary for Regulatory Activities
mITT	Modified Intent-to-Treat
NMPP	nonmenstrual pelvic pain
NRS	Numerical Rating Scale
NSAID	non-steroidal anti-inflammatory drug
PGA	Patient Global Assessment
PGIC	Patient Global Impression of Change

---

---

Term	Explanation
PLD	phospholipidosis
QTc	corrected QT (interval)
QTcF	QT interval by the Fridericia correction
SAP	statistical analysis plan
sB&B	Subject Modified Biberoglu and Behrman
SDV	source data verification
SNRI	serotonin and norepinephrine reuptake inhibitor
SSRI	selective serotonin reuptake inhibitor
TCA	tricyclic antidepressant
ULN	upper limit of normal
US	United States
W	Week
WHO-DDE	World Health Organization Drug Dictionary Enhanced

---

## 1. PROTOCOL SYNOPSIS

Study Title	SPIRIT EXTENSION: An International Phase 3 Open-Label, Single-Arm, Safety and Efficacy Extension Study to Evaluate Relugolix Co-Administered with Low-Dose Estradiol and Norethindrone Acetate in Women with Endometriosis-Associated Pain
Protocol Number	MVT-601-3103
Location	Multinational, including North and South America, Europe, Africa, New Zealand, and Australia
Study Centers	Approximately 320 sites
Study Phase	Phase 3
Target Population	Women aged 18 to 51 years diagnosed with endometriosis-associated pain
Number of Patients Planned	Approximately 800
Study Objectives	
In women with endometriosis-associated pain, the study objectives are as follows:
 
Primary Efficacy Objectives
 
To be assessed at Week 52
 
 
• To evaluate long-term efficacy of relugolix 40 mg once daily co-administered with low-dose estradiol and norethindrone acetate for up to 52 weeks, among patients who previously completed a 24-week treatment period in one of the parent studies (MVT-601-3101 or MVT-601-3102), on endometriosis-associated pain.
 
 
To be assessed at Week 104
 
 
• To evaluate long-term efficacy of relugolix 40 mg once daily co-administered with low-dose estradiol and norethindrone acetate for up to 104 weeks, among patients who previously completed a 24-week treatment period in one of the parent studies (MVT-601-3101 or MVT-601-3102), on endometriosis-associated pain.
 

	
Secondary Efficacy Objectives
 
To be assessed at Week 52 and Week 104
 
 
• To evaluate long-term efficacy of relugolix 40 mg once daily co-administered with low-dose estradiol and norethindrone acetate, among patients who previously completed a 24-week treatment period in one of the parent studies (MVT-601-3101 or MVT-601-3102), on the following: 
 
○ Function, as measured by the Endometriosis Health Profile (EHP)-30 Pain Domain;
 
○ Dysmenorrhea, as measured by the Numerical Rating Scale (NRS) for dysmenorrhea;
 
○ Patient Global Impression of Change (PGIC) for dysmenorrhea;
 
○ Nonmenstrual pelvic pain (NMPP), as measured by the NRS for NMPP;
 
○ Overall pelvic pain, as measured by the NRS;
 
 
 

	
 
○ Analgesic use;
 
○ PGIC for NMPP;
 
○ Dyspareunia, as measured by the NRS;
 
○ PGIC for dyspareunia;
 
○ Dyspareunia-related functional effects (Subject Modified Biberoglu and Behrman [sB&B]);
 
○ To determine the benefit of relugolix 40 mg once daily co-administered with 24 weeks of low-dose estradiol and norethindrone acetate compared with placebo on function measured by the EHP-30 Pain Domain;
 
○ Patient Global Assessment (PGA) for pain;
 
○ PGA for function;
 
○ Endometriosis-associated quality of life, as measured by the EHP-30 Control and Powerlessness, Social Support, Emotional Well-Being, and Self-Image domains;
 
○ Dysmenorrhea-related functional effects (sB&B);
 
○ NMPP-related functional effects (sB&B).
 
 
Safety Objectives
 
 
● To evaluate the safety of relugolix 40 mg once daily co-administered with low-dose estradiol and norethindrone acetate for up to 104 weeks, among patients who previously completed a 24-week treatment period in one of the parent studies (MVT-601-3101 or MVT-601-3102), including: 
 
○ Adverse events;
 
○ Changes in bone mineral density.
 
 
 
 
Pharmacodynamic Objective
 
 
● To evaluate the pharmacodynamic effects of relugolix 40 mg once daily co-administered with low-dose estradiol and norethindrone acetate for up to 104 weeks, among patients who previously completed a 24-week treatment period in one of the parent studies (MVT-601-3101 or MVT-601-3102), on estradiol.
 

	
Exploratory Objective
 
 
● To evaluate the benefit of relugolix 40 mg once daily co-administered with low-dose estradiol and norethindrone acetate on endometriosis-associated quality of life (EHP-30 total score), work (EHP Work Domain), and patient-reported quality of life outcomes (European Quality of Life Five-Dimension Five-Level Scale [EQ-5D-5L]) for up to 104 weeks among patients who previously completed a 24-week treatment period in one of the parent studies (MVT-601-3101 or MVT-601-3102).
 


Study Design
 
The SPIRIT EXTENSION study is an international phase 3 open-label, single-arm, long-term efficacy and safety study that will enroll eligible patients who have completed their participation in one of the phase 3 randomized, double-blind, placebo-controlled parent studies (MVT-601-3101 or MVT-601-3102). All patients will receive open-label oral relugolix 40 mg once daily co-administered with low-dose- estradiol 1.0 mg and norethindrone acetate 0.5 mg for up to 80 weeks. Approximately
	

800 women with endometriosis-associated pain will be enrolled. The objectives of the study are to evaluate long-term efficacy and safety through up to 104 weeks of treatment (including treatment during the parent study) of relugolix co-administered with low-dose estradiol/norethindrone acetate. Eligible patients will have completed participation in one of the parent studies and consented to participate in this extension study. Baseline procedures will be done at the same visit for this extension study (referred to as the “Week 24/Baseline visit” in this study) that coincides with the Week 24 visit from the parent study and will be defined as the date of completion of the last Week 24 procedure in the parent study. The Week 24/Baseline visit will include vital signs, physical examination, laboratory assessments, a 12-lead electrocardiogram (ECG), bone densitometry, patient-reported outcome assessments, and endometrial biopsy (if required). When Week 24 procedures in the parent study have been completed, the investigator will assess patient eligibility for participation in the open-label extension study. The eligibility assessment will be based on data available at the Week 24/Baseline visit. No MVT-601-3103 study procedures will be performed until the consent form for this extension study is signed.

Patients will have received their last dose of study drug in the parent study on the day prior to the Week 24/Baseline visit and will receive their first dose of study drug for this extension study in the clinic after the patient is determined to be eligible for this extension study and has provided informed consent to participate. Therefore, results of testing required for eligibility must be available on or prior to the Week 24/Baseline visit. The administration of the first dose of study drug for MVT-601-3103 will define enrollment into this study. Study participants will then take the open-label study treatment (relugolix 40 mg co-administered with estradiol 1.0 mg and norethindrone acetate 0.5 mg) orally once daily for 80 weeks. If necessary for logistical reasons (eg, delayed availability of study drug supply on site, others), and with sponsor/designee approval, the first dose of open label study drug for MVT-601-3103 may be administered up to 10 days following the parent study Week 24/Baseline visit. If the first dose of study drug is not given during this up to 10-day interval, the parent study follow-up procedures should be followed (ie, adverse event reporting, electronic diary [eDiary] completion, etc.). During the 80-week Open-Label Treatment Period and the ~30-day Follow-Up Period, patients will continue to record study treatment, assessment of pain using the NRS, menstrual bleeding, analgesic use, and the functional effects of endometriosis-associated pain (sB&B) in the eDiary. Only study-specific rescue analgesic medications should be used starting with the Week 24/Baseline visit and through the Follow-Up visit and these medications will be taken for control of pain and not prophylactically. Health-related quality of life questionnaires; PGIC for dysmenorrhea, NMPP, and dyspareunia; and PGA for pain and function will be completed during the visits on an electronic tablet or on paper, according to the Schedule of Activities (Section 1.1).

At the Week 36, Week 52, and Week 104/Early Termination visits, each patient will have an assessment of bone mineral density via dual-energy x-ray absorptiometry (DXA).

Safety will be assessed throughout the study by the monitoring of adverse events, vital signs and weight, physical examinations, clinical laboratory tests, 12-lead ECGs, mammograms (for women  $\geq 40$  years of age), endometrial biopsies, and bone mineral density with DXA.

Determination of bone mineral density by DXA at Early Termination and follow-up of findings will proceed according to the following rules:

- For Early Termination occurring between Week 24 and Week 52:
  - For Early Termination occurring before Week 36, DXA is not required at Early Termination visit unless it will aid in the assessment of an adverse event.
  - Follow-up DXA required at 6 months ( $\pm 1$  month) if most recent DXA bone mineral density loss at lumbar spine (L1-L4) or total hip was  $> 2\%$  relative to the parent study baseline.
  - For Early Termination occurring after Week 36, DXA is required at Early Termination unless a

DXA result is available from within six weeks prior to Early Termination.

- Follow-up DXA is required at 6 months ( $\pm$  1 month) if the most recent DXA scan was at Week 24 and bone mineral density loss at the lumbar spine (L1-L4) or total hip was  $> 2\%$ , relative to the parent study baseline.
- Follow-up DXA is required at 6 months ( $\pm$  1 month) if on the most recent DXA, bone mineral density loss at the lumbar spine (L1-L4) or total hip was  $> 3\%$ , relative to the parent study baseline.
- For Early Termination occurring between Week 52 and Week 104:
  - DXA is required at Early Termination unless a DXA result is available from within six weeks prior to Early Termination.
  - Follow-up DXA is required at 6 months ( $\pm$  1 month) if on the most recent DXA, bone mineral density loss at the lumbar spine (L1-L4) or total hip was  $> 7\%$ , relative to parent study baseline.
- If patients have 6-month post-treatment follow-up scans that show bone loss of  $> 1.5\%$  at the lumbar spine and/or  $> 2.5\%$  at total hip compared with parent study baseline, patients are strongly encouraged to come back to the clinic for an additional post-treatment follow-up scan 12 months from the date of the last dose of the study drug.
- If patients have 12-month post-treatment follow-up scans that show bone loss of  $\geq 3\%$  at the lumbar spine and/or total hip compared with parent study baseline, patients are referred to and strongly encouraged to see a bone specialist for further evaluation of the bone loss.

Note: When a patient is referred to a bone specialist for evaluation and management, Myovant will provide a Bone Consultation Letter to the investigator for this additional bone consult and will request the site to provide a summary of the evaluation and management plan once the consultation is complete.

Status of menstruation recovery will be documented at the Follow-up visit. Patients whose menses has not resumed as of the Follow-Up visit for whom there is no explanation for the lack of resumption (eg, medical procedure or medications) will be contacted by telephone 3 (+ 0.5) months after the Follow-Up visit to determine if menses has resumed and will be asked about factors that may affect resumption of menses. If a patient is lost to follow-up, three documented attempts should be made to contact the patient by telephone. If unable to contact the patient by telephone, a certified letter must be sent to the patient.

If the patient enrolls directly into another relugolix clinical study upon completion of the Week 104 visit, then the Follow-up visit and the follow-up procedures performed under this protocol, including the follow-up bone densitometry scan at 6 ( $\pm$ 1) months and status of menstruation recovery, may be waived.

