- Follow-up DXA is required at 6 months ( $\pm 1$  month) if on the most recent DXA, bone mineral density loss at the lumbar spine (L1-L4) or total hip was  $> 7\%$ , relative to parent study baseline.

The follow-up bone densitometry will be submitted for central reading.

Patients who experience a bone mineral density loss from the parent study Baseline of  $\geq 7\%$  at any of the anatomical sites assessed will be discontinued from the extension study and will undergo another bone densitometry scan as described above. Patients should be assessed for secondary causes of bone loss and followed up further if not improving on the 6-month follow-up scan, unless an alternative etiology has been identified.

If the patient enrolls directly into another relugolix clinical study upon completion of the Week 104 visit, then the follow-up bone densitometry scan at 6 ( $\pm 1$ ) months conducted under this protocol may be waived.

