- o For Week 24/Baseline samples, see the parent protocol (MVT-601-3101 or MVT-601-3102). At Week 104/Early Termination, collect a sample for analysis of estradiol concentrations only. On days when pharmacodynamics samples are collected, administer the study treatment after the pharmacodynamics sample collections are collected.
- p All women enrolled in the study will continue to use the patient eDiary dispensed in the parent study. Patients will complete daily eDiary entries, including NRS pain scores, menstruation information, analgesic drug use, date and time of study drug administration, and sB&B scale scores until Week 52. After Week 52, eDiary scores will be entered over four eDiary collection cycles on the following schedule: Week 57 to the Week 65 visit, Week 71 to the Week 78 visit, Week 85 to the Week 91 visit, and Week 98 to the Week 104 visit.
- q Bone densitometry (L1-L4, total hip, femoral neck) will be submitted for central reading.
- r See Section 6.5.2.6 for details on the timing and follow-up of bone densitometry.

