- s Determination of bone mineral density by DXA at Early Termination and follow-up of findings will proceed based on the timing of the Early Termination visit. For Early Termination occurring after Week 24 and before Week 36, DXA is not required at Early Termination visit unless it will aid in the assessment of an adverse event, and follow-up DXA required at 6 months ( $\pm$  1 month) if most recent DXA bone mineral density loss at lumbar spine (L1-L4) or total hip was  $>$  2% relative to the parent study baseline. For Early Termination occurring after Week 36 and before Week 52, DXA is required at Early Termination unless a DXA result is available from within six weeks prior to Early Termination, and follow-up DXA is required at 6 months ( $\pm$  1 month) if the most recent DXA scan was at Week 24 and bone mineral density loss at the lumbar spine (L1-L4) or total hip was  $>$  2% or most recent DXA result was after Week 24 and bone mineral density loss at the lumbar spine (L1-L4) or total hip was  $>$  3%, relative to the parent study baseline. For Early Termination occurring between Week 52 and Week 104, DXA is required at Early Termination unless a DXA result is available from within six weeks prior to Early Termination, and follow-up DXA is required at 6 months ( $\pm$  1 month) if on the most recent DXA, bone mineral density loss at the lumbar spine (L1-L4) or total hip was  $>$  7%, relative to parent study baseline.

- t Endometrial biopsies are to be done per instructions in the parent study. Procedures for handling and shipping biopsy samples to the central laboratory for analysis are described in the Investigator Site File. An endometrial biopsy will have been performed at the parent study Week 24 visit for all patients who participated in MVT-601-3101 only (see MVT-601-3101 protocol for details) and at Week 52 and Early Termination visit for all patients. This procedure is not required at the Early Termination visit in patients whose last dose of study drug was taken during Week 32 or earlier or within four weeks after completion of the Week 52 endometrial biopsy. However, the procedure may be done if it will aid in the evaluation of an ongoing adverse event. An endometrial biopsy at Week 104 is recommended for all patients who complete the open-label extension; however, patients will have the option to opt out.

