- aa Collect adverse events from the time that the first dose of study drug for MVT-601-3103 is administered. Adverse events with onset prior to the first dose of study drug for MVT-601-3103 should be reported as an adverse event in the parent study (MVT-601-3101 or MVT-601-3102). If events originating in the parent study are ongoing at the time of the first dose of study drug for MVT-601-3103, please see the Case Report Form Completion Guidelines for instructions for recording the follow-up status.
- bb Patients whose menses have not resumed as of the Follow-up visit for whom there is no explanation for the lack of resumption (eg, medical procedure or medications) will be contacted by telephone 3 (+0.5) months after the Follow-Up visit to determine if menses has resumed and questioned about factors that may affect resumption of menses. If a patient is lost to follow-up, three documented attempts should be made to contact the patient by telephone. If unable to contact the patient by telephone, a certified letter must be sent to the patient.
- cc A telephone call will be performed at Weeks 57, 71, 85, and 98. The following activities should be completed: a concomitant medication review, evaluation of adverse events, and a review of eDiary and study medication compliance.
- dd For patients  $\geq 40$  years old at the time of the Week 52 visit, Week 104 visit, or Early Termination visit only. See Section 6.5.2.9.
- ee See Section 6.5.2.6, Section 6.5.2.7, and Section 6.5.2.8 to determine if additional follow-up is required.

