#### Exclusion Criteria

1. Has had a surgical procedure for treatment of endometriosis at any time during the parent study (MVT-601-3101 or MVT-601-3102);
2. Has any chronic pain or frequently recurring pain condition, other than endometriosis, that is treated with opioids or requires analgesics for  $\geq 7$  days per month;
3. Has a weight that exceeds the weight limit of the DXA scanner or has a condition that precludes an adequate DXA measurement at the lumbar spine and proximal femur (eg, bilateral hip replacement, spinal hardware in the lumbar spine);
4. Has a Z-score  $< -2.0$  or has a  $\geq 7\%$  decrease in bone mineral density from the parent study Baseline at lumbar spine, total hip, or femoral neck based on the parent study Week 24 DXA assessment of bone mineral density;
5. Anticipated to use any prohibited medications as detailed in Section 5.10.1;

6. Has any contraindication to treatment with low-dose estradiol and norethindrone acetate, including:
  - a. Known, suspected, or history of breast cancer;
  - b. Known or suspected estrogen-dependent neoplasia;
  - c. Active deep vein thrombosis or pulmonary embolism, or history of these conditions prior to the Week 24/Baseline visit;
  - d. History of or active arterial thromboembolic disease, including stroke and myocardial infarction;
  - e. Known anaphylactic reaction or angioedema or hypersensitivity to estradiol or norethindrone acetate;
  - f. Known protein C, protein S, or antithrombin deficiency, or other known thrombophilia disorders, including Factor V Leiden;
  - g. Migraine with aura;
  - h. History of porphyria;
7. Has current active liver disease from any cause;
8. Has a systemic autoimmune disease (eg, systemic lupus erythematosus, Sjogren's syndrome, rheumatoid arthritis, polymyositis, systemic sclerosis, psoriasis, psoriatic arthritis, vasculitic syndromes, etc); psoriasis not requiring or anticipated to require systemic therapy is permitted;
9. Had any of the following clinical laboratory abnormalities at the parent study Week 20 visit or, if available, any subsequent visit in one of the parent studies (MVT-601-3101 or MVT-601-3102):
  - a. Alanine aminotransferase (ALT) or aspartate aminotransferase (AST) > 2.0 times the upper limit of normal (ULN); or
  - b. Bilirubin (total bilirubin) > 1.5 x ULN (or > 2.0 x ULN if secondary to Gilbert syndrome or pattern consistent with Gilbert syndrome);

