  - If the patient has a  $\geq 7\%$  loss of bone mineral density at lumbar spine, total hip, or femoral neck compared with the parent study Baseline;
  - If the patient, in the opinion of the investigator or the medical monitor, is grossly noncompliant with the protocol's requirements. Gross noncompliance includes  $< 75\%$  compliance with the study drug over  $> 2$  consecutive months; missing multiple study visits; and persistent ( $> 2$  consecutive months) noncompliance ( $< 50\%$  of the required number of days) with eDiary completion up to Week 52 or persistent ( $\geq 2$  eDiary collection cycles) noncompliance ( $< 50\%$  of the required number of days) with eDiary completion from Week 52 to Week 104. Investigators will follow up with the patient and encourage compliance with study drug or eDiary prior to discontinuing her from the study;
  - If the patient becomes pregnant at any time after providing a signed informed consent form, the patient must be withdrawn immediately (see Section 7.8 for information on pregnancy reporting);
  - Evidence of malignant breast lesion(s) or breast carcinoma on Week 52 or Week 104/Early Termination or most recent mammogram or additional breast imaging (see Section 6.5.2.9 for more information on mammogram at Week 52 or Week 104/Early Termination);

Should a patient fail to attend the clinic for a required study visit within the protocol-defined window, the site should attempt to contact the patient and reschedule the missed visit as soon as possible. The site should also counsel the patient on the importance of maintaining the assigned visit schedule and determine whether the patient can and/or should continue in the study based on previous noncompliance. In cases where the patient does not return for the rescheduled visit or cannot be reached to reschedule the missed visit, the site should make every effort to regain contact with the patient. The site should attempt at least three documented telephone calls and if necessary, a certified letter to the patient's last known mailing address so that they can appropriately be withdrawn from the study with a primary reason of "Lost to Follow-up."

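### The listed 6-month follow-up DXA triggers leave out the femoral neck, one of the three sites in the 7% bone-loss withdrawal rule

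*Protocol*

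**What the plan says.** Three sets of rules bear on the point.

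**Withdrawal.** Section 4.5 removes a woman from therapy for a 7% or greater "loss of bone mineral density at lumbar spine, total hip, or femoral neck compared with the parent study Baseline". Exclusion criterion 4 in Section 4.3.1 bars entry on the same three sites and the same limit, a 7% or greater "decrease in bone mineral density from the parent study Baseline at lumbar spine, total hip, or femoral neck" on the Week 24 scan of the parent study.

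**6-month rescan after Early Termination.** The synopsis (Study Design, DXA rules) and footnote s of Table 1-1 list the triggers by time of termination:

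- Before Week 36: loss above 2% at spine or hip on the most recent scan.
- Weeks 36 to 52: loss above 2% if the last scan was at Week 24, "or most recent DXA result was after Week 24 and bone mineral density loss at the lumbar spine (L1-L4) or total hip was" above 3%.
- Weeks 52 to 104: rescan "if on the most recent DXA, bone mineral density loss at the lumbar spine (L1-L4) or total hip was" above 7%.

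The femoral neck appears in none of them.

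**Section 6.5.2.6.** In the Amendment 2 text, patients with a loss of 7% or more "at any of the anatomical sites assessed will be discontinued from the extension study and will undergo another bone densitometry scan as described above". The next sentence has them "followed up further if not improving on the 6-month follow-up scan", unless another cause has been found. In the current version, footnote r reads "See Section 6.5.2.6 for details on the timing and follow-up of bone densitometry" and footnote ee reads "See Section 6.5.2.6, Section 6.5.2.7, and Section 6.5.2.8 to determine if additional follow-up is required". Only the opening of the current Section 6.5.2.6 is visible, and it stops before any follow-up rule.

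**The concern.** The femoral neck is scanned, is a named safety endpoint and is a withdrawal site, yet no listed rescan trigger mentions it. After Week 52 the trigger rises from 3% to 7%, the same figure as the withdrawal limit. That suggests it was meant to catch women stopped for bone loss, but it covers only two of the three sites and only values strictly above 7%.

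The synopsis presents its list as the rules by which follow-up proceeds, so a site could reasonably treat it as complete. Such a site could omit the post-treatment scan for a woman withdrawn for femoral-neck loss, and recovery at the site that caused her withdrawal would go undocumented. The on-treatment scan that showed the loss is not affected.

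**Working it through.** No plan figure has to be reproduced. The check sets the rules side by side.

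**Inputs.** Let S, H and F be the percentage losses from parent study Baseline at lumbar spine, total hip and femoral neck.

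- Withdrawal (Section 4.5): max(S, H, F) ≥ 7.
- Listed trigger, termination Weeks 36 to 52, last scan after Week 24 (synopsis, footnote s): max(S, H) > 3.
- Listed trigger, termination Weeks 52 to 104 (same places): max(S, H) > 7.
- Trigger added by the proposed sentence: max(S, H, F) ≥ 7.

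**Where withdrawal applies but no listed trigger is met.**

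- Weeks 36 to 52: S ≤ 3 and H ≤ 3, so withdrawal can come only from F ≥ 7. A spine or hip loss of 7% or more exceeds 3% and always triggers.
- Weeks 52 to 104: S ≤ 7 and H ≤ 7, with either F ≥ 7 or S or H exactly 7.0.

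**Cases (S / H / F, %).** Every case meets the withdrawal rule.

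| Termination | S / H / F | Listed trigger met | Met with added sentence |
|---|---|---|---|
| Weeks 36–52 | 3.0 / 3.0 / 7.5 | no | yes |
| Weeks 36–52 | 3.1 / 3.0 / 7.5 | yes | yes |
| Weeks 36–52 | 6.5 / 6.5 / 7.5 | yes | yes |
| Weeks 36–52 | 7.0 / 5.0 / 5.0 | yes | yes |
| Weeks 52–104 | 3.0 / 3.0 / 7.5 | no | yes |
| Weeks 52–104 | 6.5 / 6.5 / 7.5 | no | yes |
| Weeks 52–104 | 7.0 / 7.0 / 7.5 | no | yes |
| Weeks 52–104 | 7.0 / 5.0 / 5.0 | no | yes |
| Weeks 52–104 | 5.0 / 7.0 / 5.0 | no | yes |
| Weeks 52–104 | 7.1 / 5.0 / 5.0 | yes | yes |

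Losses of 6.5 / 6.5 / 7.5 show how the gap widens with time: they trigger a rescan before Week 52 but not after it.

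**Before Week 36.** The gap is nearly closed. The last scheduled scan is then the one at Week 24, and a loss of 7% or more on it at any of the three sites bars entry under exclusion criterion 4. The same reasoning disposes of the Weeks 36 to 52 branch in which the last scan was at Week 24.

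**The Amendment 2 sentence.** It covers any assessed site and a loss of exactly 7%. Its closing reference back could mean the manner and timing of the scan, or the triggers listed before it. The next sentence takes for granted that these patients have a 6-month scan, which favours the first reading.

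**The case against.** The strongest reply is that Section 6.5.2.6 governs and the lists only summarise it. Footnotes r and ee and Sections 4.1 and 6.3 all send the site there. The one complete copy, from Amendment 2, is most naturally read as requiring a rescan for every woman discontinued at 7% or more at any assessed site. The follow-up rules of the current copy cannot be seen, and text that is not visible cannot be called missing. This stands. A reader might infer that women withdrawn for femoral-neck loss go without a scan, and the documents do not support that. What remains is that the synopsis and footnote s state a narrower rule than the one the section appears to intend.

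A second reply is that stopping rules and rescan rules need not match. The 2% and 3% triggers plainly do not mirror 7%. The 12-month scan and the bone-specialist referral in the synopsis are also keyed to spine and hip. This is fair as far as it goes, but no reason for leaving out the femoral neck is given in the text shown, and the Amendment 2 sentence points the other way.

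A third reply is that other safeguards exist. Section 6.4 allows an unscheduled DXA with sponsor approval. Under the Amendment 2 text of Sections 7.1.1 and 7.2, an abnormality judged clinically significant because it requires stopping the drug is an adverse event, followed until it resolves, stabilises or becomes chronic. These provisions soften the consequence, but none of them prescribes a 6-month DXA.

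**Conclusion.** The mismatch is real in the visible current text, and its severity is low. The substance is a femoral-neck withdrawal with spine and hip losses both at most 3% (termination Weeks 36 to 52, last scan after Week 24) or both at most 7% (Weeks 52 to 104). Exactly 7.0% at spine or hip after Week 52 is a rare boundary case and carries little weight.

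The number of women cannot be estimated from the documents. It is zero if the current Section 6.5.2.6 carries an unconditional rescan rule and sites follow that section. Even then, the synopsis and footnote s should agree with it.

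A reader might also infer that the bone density results are compromised. They are not: the comparison of Week 52 lumbar spine change with -2.2% uses on-treatment spine scans, and the post-treatment rescan rule does not touch it. This is a point of patient follow-up, not of inference.

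**What to change.** Keep every existing threshold. In the synopsis and in footnote s, and in Section 6.5.2.6 unless it is already unconditional, add:

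> A follow-up DXA 6 months (± 1 month) after the last dose is also required for any patient whose most recent on-treatment DXA shows a loss of 7% or more from parent study baseline at the lumbar spine, total hip or femoral neck.

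With this sentence, every withdrawal under the 7% rule leads to a listed 6-month scan, including the exact 7.0% case. It also states which scan counts and from when the 6 months run.

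The cost is one sentence of amendment text and a few extra scans, all in women already withdrawn for bone loss and apparently intended by the Amendment 2 text. The sentence secures the 6-month scan only. The criteria for the 12-month scan and the specialist referral stay keyed to spine and hip. The laboratory tests for incomplete recovery in Section 6.5.2.4 are not tied to a site in the text shown and need no change.
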